watch the educational materials. A research assistant will help them use the system and offer counseling/explanations for the materials. The patient and caregiver will be given a week to learn these materials (Figure 3). Further counseling/explanations will be given, if necessary. After a week, the research assistant will ask the participants whether they have further questions on the educational materials. The research assistant will answer their remaining questions until the participants are satisfied with the explanations. Then the participants will be asked to take the computerized knowledge testing system again. Further educational materials will be offered, if necessary. The testing and educational procedures will continue until the participants' stroke and OT knowledge has reached a satisfactory level. The research assistant will make sure that the participants understand all the fundamental knowledge of stroke and OT, which will be pre-determined by our experts.

[figure not shown]

Figure 3. The procedures of testing knowledge of stroke/OT and offering educational materials and counseling.

We expect that the whole procedure will take about 2 to 3 weeks (i.e., two to three times of education). The time that the patient/caregiver devotes to learning the related materials will be recorded. We will also document the difficulties/questions raised by the participants. Such information will be useful for further improving the efficiency of the system.

The participants in the control group will not be given the results of testing. However, oral explanations will be given by the research assistant if they have questions about the testing. These participants in the control group will be offered additional rehabilitation programs to serve as a placebo. The time of the additional rehabilitation program will be similar to the time that the participants spend taking part in the experimental group, which we expect to be about 2 hours per week for 3 consecutive weeks.

Data analysis

Baseline characteristics will be reported by descriptive statistics (e.g., mean and SD for continuous variables, or frequency tabulations for categorical variables) for each group. Homogeneity of both groups at the baseline (time 1) will be examined using a Student's t test or Mann-Whitney U test where appropriate. If there are between significant differences between both groups, statistical control (e.g., analysis of covariance, ANCOVA) will be applied for further analysis of effectiveness.

The primary analysis of effectiveness (full-analysis set) will consist of a comparison of the change scores between time 2 to time 1 and time 3 to time 2 in stroke and OT knowledge. Analysis of variance (ANOVA) will be used to compare the change scores between groups. The analyses will be adjusted using ANCOVA for any significant differences at baseline. Intention-to-treat analysis will be applied. Alpha level will be set at 0.05. The statistical analyses will be done by use of SPSS (version 16.0).

Phase 5: Developing a patient-centered OT program.

We will develop a patient-centered, individual tailored OT program on the basis of both a theoretical framework and the opinions of clinical experts. We will employ Steward et al.'s model³⁰ to develop the patient-centered OT program. The 6 main components of Steward et al.'s model include: (1) exploring both disease and illness experience, (2) understanding the whole person, (3) finding common ground, (4) incorporating prevention and health promotion, (5) being realistic, and (6) enhancing the patient-clinician relationship.³⁰ We will develop detailed procedures for administering all the components, as an individual and as a whole. The computerized adaptive stroke and OT knowledge and education systems will be included in the component of "exploring both disease and illness experience." We will invite 5 occupational therapists with sufficient clinical experience and 2 psychiatrists to review the procedures of the patient-centered, tailored OT program. Their comments will be used to revise the procedures until agreement has been reached.

After the procedures for the patient-centered OT program are developed, we will test the feasibility of the program. We will make revisions where necessary. The clinical experts will be consulted if necessary.

Phase 6: Examining the effectiveness the patient-centered OT program on 100 patients.

Subjects:

100 sub-acute patients (including inpatients and outpatients) will be recruited from the National Taiwan University Hospital. The patients will meet the criteria (both inclusion and exclusion criteria) mentioned in the phase 4 study. Their caregivers will also be invited to participate.

Power analysis

A difference of 2 points (about 10%) on the Barthel index in favor of the experimental group will be regarded as clinically relevant.⁵⁷ In addition, we expect that about 70% of the participants will complete all assessments. Therefore, about 50 patients will be required for each arm of the trial to achieve a sufficient statistical power of 80%.

Procedure:

The patients will be randomly assigned into an experimental group (receiving the patient-centered program) or a control group (receiving additional rehabilitation). Allocation concealment will be applied. All participants will be assessed by trained raters at the beginning of the study, 4 weeks after inception of the study, 3 months after inception of the study, and 1 year after inception of the study. The raters will be unaware of study-group assignment. The cost of each group will be recorded.

We will determine cost-effectiveness by relating the costs to the effects of the program. The effects will be expressed as quality-adjusted life years (QALYs), which are measured by the EQ-5D. The costs include the costs related to resource use of primary care clinicians, secondary care appointments, admissions to health care facilities, community-based support, and individual out-of-pocket expenditure (direct costs). The direct cost estimates will be based on the costs of hospital stay and follow-up rehabilitation care. Medication costs and costs related to assistive devices and adaptations in and around the house will also be included. The costs of productivity losses (indirect costs) will not be counted because most stroke patients are retired. The incremental cost-effectiveness ratio will be calculated by dividing the mean difference in costs by the mean difference in effect (as measured by the EQ-5D) between the two groups. Costs will be evaluated by having each patient keep a cost diary for the first 24 weeks after randomization. A research assistant will check the diary every other day to ensure the integrity of recording (including the time spent on each kind of professional care). The hourly costs of specialists (including physicians, physical therapists, occupational therapists, and speech and language therapists) will be calculated using the salary schedules at the National Taiwan University Hospital.

The patient-centered program will last for 6 weeks. We expect that the therapist will spend 2-4 hours on each patient per week. For the control group, we will provide 2-hour OT per week in addition to the original OT. The content of the original and additional OTs will be recorded for both groups.

Neurobehavioral conditions of the patients:

The NIHSS⁵¹ will be used to indicate stroke severity in the study sample. The NIHSS is a well validated and commonly used stroke impairment scale that sums the scores from individual elements of the neurological examination to provide an overall stroke severity score.^{51,58}

The stroke rehabilitation assessment of movement (STREAM)⁵⁹ instrument consists of 30 items that are equally distributed among 3 subscales: upper-limb motor function, lower-limb motor function, and mobility. Motor function is scored on a 3-point scale (0: unable to perform the test movement; 1: able to only partially perform the test movement; and 2: able to complete the test movement). Mobility is scored on a 4-point scale similar to that used for scoring limb movements except that a category has been added to allow for independence with the help of a mobility aid. Thus, the maximum raw total STREAM score is 70, with each of the limb subscales scored out of 20 points and the mobility subscale scored out of 30 points. We have validated the STREAM thoroughly in stroke patients.⁶⁰⁻⁶⁴

Primary outcome measures:

The Frenchay Activities Index (FAI)⁶⁵ was developed to measure social function and instrumental activities of daily living following stroke. It comprises 15 items related to normal activities: preparing

meals, washing up, washing clothes, light housework, heavy housework, local shopping, social outings, walking outside for more than 15 minutes, actively pursuing hobbies, driving/bus travel, outings/car rides, gardening, household/car maintenance, reading books, and gainful employment. The total possible score of the FAI ranges from 0 to 45. The FAI is reliable and valid in assessing social function for patients with stroke.⁶⁵⁻⁶⁷

The Barthel ADL Index (BI)⁶⁸ and the FAI scores can be combined to represent comprehensive activities of daily living (CADL) function, representing the entire continuum of disability.⁶⁹ The CADL contains 10 items of the BI and 13 items of the FAI (with 2 misfit items of the FAI deleted to fit the Rasch model).⁶⁹ The Rasch-transformed interval score of the CADL proposed by Hsueh et al.⁶⁹ will be used in this study.

We will also use the computerized adaptive ADL test which was developed by our research group. The computerized adaptive ADL test is efficient and valid to assess ADL and IADL in stroke patients.⁷⁰ The computerized adaptive ADL test is particularly useful for the patients in our country because it is the only ADL/IADL measure developed for stroke patients in Taiwan. Particularly, some IADL items are specific to cultural differences.⁷¹

Secondary outcome measures:

The EuroQol is a generic measure of quality of life (QoL) and consists of a health status profile in five domains (EQ-5D), including two that are directly related to self-care and mobility.⁷² The EuroQol has been validated for use in stroke patients.⁷³ The advantage of the EuroQol is that it can be transformed into a utility score, allowing cost-utility analysis.^{43, 72}

The Stroke-Specific Quality of Life (SS-QOL)¹ is the first HRQOL measure designed to capture all domains meaningful for stroke patients. The original developers constructed the domains and items of the SS-QOL on the basis of patient interviews. It originally included 49 items from 12 domains. We have reported that construct validity of the 12-domain SS-QOL is well supported for measuring HRQOL in ischemic stroke patients.⁷⁴

Treatment protocols for the experimental and control groups:

The patients assigned to the experimental group will first receive the computerized adaptive knowledge testing system. They will be then given adaptive educational materials provided by the educational system according to their testing results. The participants will be instructed to read or watch the educational materials. A research assistant will help them use the system and offer counseling/explanations for the materials. The patient and caregiver will be given a week to learn these materials. Further counseling/explanations will be given, if necessary. After a week, the research assistant will ask the participants whether they have further questions on the educational materials. The research assistant will answer their remaining questions until the participants are satisfied with the explanations. Then the participants will be asked to take the computerized knowledge testing system again. Further educational materials will be offered, if necessary. The testing and educational procedures will continue until the participants' stroke and OT knowledge has reached a satisfactory level. The research assistant will make sure that the participants understand all the fundamental knowledge of stroke and OT, which will be pre-determined by our experts.

We expect that the whole procedure will take about 2 to 3 weeks (i.e., two to three times of education). The time that the patient/caregiver devotes to learning the related materials will be recorded. We will also document the difficulties/questions raised by the participants. Such information will be useful for further improving the efficiency the system.

The participants in the control group will not be given the results of testing. However, oral explanations will be given by the research assistant if they have questions about the testing. These participants in the control group will be offered additional rehabilitation programs to serve as placebo. The time of the additional rehabilitation program will be similar to the time that the participants spend taking part in the experimental group, which we expect to be about 2 hours per week for 3 consecutive weeks.

Data analysis:

Baseline characteristics will be reported by descriptive statistics (e.g., mean and SD for continuous variables, or frequency tabulations for categorical variables) for each group. Homogeneity of both groups at the baseline (time 1) will be examined using a Student's t test or Mann-Whitney U test where appropriate. If there are between significant differences between both groups, statistical control (e.g., analysis of covariance, ANCOVA) will be applied for further analysis of effectiveness.

The primary analysis of effectiveness (full-analysis set) will consist of a comparison of the change scores between time 2 to time 1 and time 3 to time 2 in primary and secondary outcome measures. Analysis of variance (ANOVA) will be used to compare the change scores between groups. The analyses will be adjusted using ANCOVA for any significant differences at baseline. Intention-to-treat analysis will be applied. Alpha level will be set at 0.05. The statistical analyses will be done by use of SPSS (version 16.0).

Incremental cost-effectiveness ratios will be calculated as cost per QALY to assess the cost-effectiveness of the different programs.

(F) Anticipated Results

We expect that the patients and caregivers' original knowledge of stroke and OT would be limited or modest. Our adaptive knowledge and education system will efficiently improve their knowledge of stroke and OT. We anticipate that the CATs for stroke and OT knowledge can reach an overall reliability above 0.95 (i.e., excellent reliability) and require less than 10 minutes to administer or test fewer than 20 items to ensure its efficiency.

Furthermore, the patient-centered OT program using the adaptive knowledge and education system will improve ADL independence in stroke patients. The patient-centered OT program will be cost-effective in increasing ADL function and quality-adjusted life years.

Significance:

1. The adaptive knowledge and education system will be useful for clinicians to promote stroke and OT knowledge for stroke patients and their families.
2. There is no computerized adaptive stroke and OT knowledge and education system yet. Our system could be the first one in the world.
3. The adaptive knowledge and education system may be so efficient that it can facilitate the administration of the patient-centered OT approach in busy clinical settings. Thus, the patient-centered OT approach will be feasible and effective.
4. We will develop clinical guidelines on the basis of the patient-centered OT program to disseminate this program to daily clinical practice.
5. We hope that our project will allow us to combine patient-centered care and evidence-based medicine while addressing the imperatives of cost effectiveness and utility.

Anticipated challenges:

We may face one challenge to collecting the cost of rehabilitation (including both direct and indirect costs). To address this issue, we will consult with an expert in health economy ([name]^{75, 76}) before the inception of our study.

In addition, we will consult [name], who has supervised our team for more than 10 years, for calculation of quality-adjusted life year.

(G) Human Subjects

We will obtain the approval of the Institution Review Boards of the National Taiwan University Hospital. We propose to recruit about 700 eligible stroke patients and 450 caregivers during the study period. Clinical information about the patients will be obtained from medical records. Assessments of functional outcomes and related health status will be conducted using personal interview or performance rating scales. All the assessments will be administered by experienced occupational therapists or physical therapists. In some neurobehavioral assessments, some movements difficult for the patients will, unavoidably, have to be performed. In addition, some patients might feel that there are too many questions. An invitation letter will be sent out to obtain written informed consent from each participant. The letter will explain, plainly and in simple terms, the purposes of the study, the procedures, and the risks and benefits in this project, as well as the process of informed consent.

The potential risk in this research is minimal. In Phases 4 and 6, some patients will need to have their motor function examined and might feel insecure when asked to execute certain movements (e.g., climbing stairs). Procedures to minimize the risk will include careful training and safety education for the therapists.

All the data collected for this project will remain confidential. The participants' data will be kept in locked file cabinets located in the PI's office, accessible only to the study personnel.

The benefits for the participants/caregivers and/or their clinical therapists will be the results of this study. These results will help both clinicians and researchers to promote patient-centered care and evidence-based medicine.

(H) Gene Recombination

NA

(I) Animal Investigations

NA

(J) Potential Hazards

The whole project requires interviews with patients and caregivers. We will also examine the neurobehavioral performance of the patients. There will be no potential risks for patients and caregivers. However, the patients might feel tired sometimes. We will allow the patients to rest if necessary. Some stroke patients might lose their balance and thus suffer injury. To avoid this, all personnel, as mentioned in section G above, will receive extensive training on how to anticipate and avoid such occurrences.

(K) References:

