Form Section 5 - Research Plan

Complete this section in the order of all the following components: (A) Specific Aims, (B) Statement of Qualifications for Innovative Research Grant Award, (C) Background and Significance, (D) Previous and Current Studies, (E) Research Design and Methods, (F) Anticipated Results, (G) Human Subjects, (H) Gene Recombination, (I) Microbes in Risk Group 2, 3, 4, (J) Animal Investigations, (K) Potential Hazards, and (L) References. Please specify each item in separate paragraphs.

(A) Specific Aims

Overall aims: This project has two primary purposes. The first purpose is to develop a computerized adaptive knowledge and education system for testing and improving the patient's and caregiver's knowledge on both stroke and occupational therapy (OT). The second purpose is to develop a patient-centered, individual tailored OT program on the basis of the computerized adaptive knowledge and education system and examine its effect on ADL function in stroke patients.

Specific aims (as described according to the timeline of this project):

Phase 1 - First half year (0-0.5; 0.5 year):

1. To develop a 100-item pool for stroke and OT knowledge, respectively. All 200 items will be designed to be easy-to-understand for the patients and encompass the full spectrum of knowledge.
2. To develop educational materials using multimedia for stroke and OT knowledge. All the items of stroke and OT knowledge and their corresponding educational materials will be matched.

Phase 2 - Second half of the first year to the first half of the second year (0.5-1.5; 1 year):

1. To administer the 200 items on caregivers and patients with as wide a range of severity as possible. Because of the endurance/acceptability of patients, each patient will be interviewed with about 100 items randomly selected from the 200 items. Each caregiver will be interviewed for all 200 items. In addition, responses from 200 patients and 200 caregivers for each item are needed for data analysis. Thus, 400 patients and 200 caregivers will be interviewed.
2. To apply the educational materials for 100 patients and 100 caregivers. We will make sure that all the educational materials will be easy-to-understand for patients and caregivers.

Phase 3 - The second half of the second year (1.5-2; 0.5 year):

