We expect that 200 items will be constructed for each item pool. A total of 400 items will be developed for both the stroke and OT knowledge-item pools.

Procedures of Developing Educational materials:

Figure 2 (the bottom part) also shows the content generation and review procedures. The content and design features of the educational information will be prepared according to best practice recommendations.³⁴ This includes features such as appropriate layout, organization, and typography; appropriate use of illustrations and media; and the incorporation of features that facilitate learning and motivation.

For the development of content, the educational materials will be fully linked with the domains and items of stroke and OT knowledge. We will use various media, including written, audio, and video media, where appropriate, to achieve ultimate learning effects. All educational materials will undergo an initial set of 5 cognitive interviews. The materials will be revised, if necessary, to increase clarity, appropriateness, and relevance for the patients/caregiver.

Phase 2: Field testing of the knowledge items and educational materials on caregivers and stroke patients with characteristics as diverse as possible*Subjects:*

From the 6th to the 18th month, 400 patients (half inpatients and half outpatients) will be recruited if they meet the following criteria: (1) diagnosis (International Classification of Diseases, ninth revision, clinical modification [ICD-9] codes) of cerebral hemorrhage (ICD-9, 431) or cerebral infarction (ICD 9, 434), (2) absence of any other major disease affecting premorbid ADL independence and mobility (e.g., severe rheumatologic arthritis), (3) ability to follow instructions and complete the interviews, and (4) ability to give informed consent personally. We will exclude patients with cognitive impairment (Mini-Mental State Examination (MMSE)⁴⁷ scores < 20). In addition, we will invite 200 caregivers to participate in this study.

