The reasons for recruiting 400 patients are described as follows, although a theory-based mathematical function to calculate sample sizes needed for IRT is largely lacking.⁴⁸ First, because of the endurance/acceptability of patients, each patient will be administered about 100 knowledge items randomly selected from the 200 items and their corresponding educational materials. In addition, at least 200 responses for each item, or responses from 200 patients, are strongly recommended for data analysis.^{49, 50} Thus, about 400 patients will be interviewed.

To ensure selection of patients with a broad range of severity and days after stroke onset, we will use a stratified sampling method. Two stratifying variables will be considered. One is stroke severity (using the National Institutes of Health Stroke Scale [NIHSS]⁵¹ as 4 strata: mild [NIHSS 0-5], moderate [6-10], severe [11-20], and very severe [>20]). The other is time after stroke onset (3 strata: 0-3 months, 3-12 months, and > 12 months). We will determine whether the patients cover the entire spectrum of stroke severity and days after onset after one year of data collection. If not, we will later recruit patients who are less representative to ensure adequate representation of the stroke population.

Procedures:

All 200 items and their corresponding educational materials developed in Phase 1 will be coded and saved in personal computers (PC, a touchscreen notebook). We will randomly select items from the item pools to administer on each patient or caregiver. On average, each patient will be tested with about 100 items by face-to-face interview. After the testing, if a participant fails on some items, the corresponding educational materials will be presented. However, each session will be shorter than 1.5 hours to prevent patient/caregiver discomfort and fatigue. The patients/caregivers will be able to take a rest during the testing, if necessary. If a patient/caregiver cannot complete more than 60 items in one session, the patient will be invited to be tested again on another day, but within a week.

The data collection will be carried out by research assistants (full-time or part-time; occupational therapists or research nurses). All items will be administered by face-to-face interview. To avoid any possible interference during the interviews, all the interviews will be administered in a quiet room (e.g., individual treatment room or counseling room).

Data analysis

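### Phase 1 gives the item pool as 400 items, the aims and Phase 2 as 200; the 400-patient sample meets its target of 200 patient responses per item only with 200 items

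*Protocol*

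**What the plan says.** The protocol gives the size of the item pool in three places.

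- **Section A, Specific Aims, Phase 1:** "To develop a 100-item pool for stroke and OT knowledge, respectively", followed by "All 200 items will be designed to be easy-to-understand for the patients and encompass the full spectrum of knowledge". That is 100 per pool and 200 in all.
- **Section E, Phase 1, Procedures of Item Pool Development (closing paragraph):** "We expect that 200 items will be constructed for each item pool. A total of 400 items will be developed". That is 200 per pool and 400 in all.
- **Section E, Phase 2:** under Subjects, "each patient will be administered about 100 knowledge items randomly selected from the 200 items". Under Procedures, the 200 items loaded on the notebooks are described as the ones that Phase 1 produced.

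The Phase 2 Subjects section justifies the 400 patients on the ground that "at least 200 responses for each item, or responses from 200 patients, are strongly recommended for data analysis". The Specific Aims (Phase 2) call for 200 patient responses and 200 caregiver responses to each item, with every caregiver answering all 200 items.

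**The concern.** Phase 1 cannot hand over both 400 and 200 items, and the text describes nothing in between that would turn one into the other. The cognitive interviews in Phase 1 lead to rewording and re-interviewing; no rule drops an item. The deletion rules (factor loading below 0.4, infit or outfit above 1.3) stand in the Phase 2 data analysis and apply after the responses have been collected, so they cannot reduce the number of items fielded.

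The figure of 400 is not self-evidently a slip. It is stated consistently, per pool and in total. The same section asks for at least 50 items per domain without fixing the number of domains: two domains would give 100 items per pool, four would give 200.

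The number of items in the field sets the number of responses per item. Those responses calibrate the item bank, which feeds the adaptive test and its simulation in Phase 3, the outcome in Phase 4 and the knowledge-testing component of the Phase 6 programme.

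**Working it through.** **Inputs.** Patients N = 400, items per patient k = about 100, and target responses per item r = 200 (all from Phase 2, Subjects). Total items M = 200 (Specific Aims; Phase 2) or 400 (Phase 1 procedures).

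**Step 1. Reproduce the plan's figure.** N = r × M / k.
- M = 200: 200 × 200 / 100 = 400 patients, which matches the stated sample exactly.
- M = 400: 200 × 400 / 100 = 800 patients, which does not match.

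**Step 2. Expected patient responses per item.** N × k / M.
- M = 200: 400 × 100 / 200 = 200, the target with no margin.
- M = 400: 400 × 100 / 400 = 100, or 50% of the target. With 400 patients, reaching 200 would need 200 × 400 / 400 = 200 items per patient, twice the number that the protocol sets with patient endurance in mind.

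**Step 3. Effect on precision if 400 items were fielded.** The standard error of an item difficulty scales roughly as 1/√(responses), for the same mix of respondents.
- Patients alone: √(200/100) = 1.41, about 41% larger.
- Patients and caregivers pooled, with caregivers answering all 400 items (an assumption): responses fall from 200 + 200 = 400 to 100 + 200 = 300, and √(400/300) = 1.15, about 15% larger.
- Pooled, with each caregiver answering 200 of the 400 (an assumption): caregivers give 200 × 200 / 400 = 100 per item, so the total falls from 400 to 200 and the increase is again about 41%.

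The protocol does not say whether patients and caregivers are calibrated together. Because the aims ask for 200 responses from each group separately, the patient target would be missed in every case.

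**Step 4. Spread with 200 items under simple random selection.** Each patient receives a given item with probability 100/200 = 0.5, so the count per item is binomial (400, 0.5).
- Mean 200; SD = √(400 × 0.5 × 0.5) = 10.
- Chance that an item reaches at least 200: 0.52. Chance that it falls below: 1 − 0.52 = 0.48, or about 0.48 × 200 = 96 of the 200 items.

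The shortfalls are mostly small, since one SD is 10/200 = 5% of the target. But a figure described as a minimum for each item is met by only about half of the items.

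**The case against.** The best counter-argument is that the Phase 1 paragraph is the outlier. The aims and Phase 2 agree on 200, the stated sample is reproduced exactly with 200, and the 400 is introduced only as an expectation. On that reading the sample-size reasoning is sound and one paragraph carries a wrong count. This stands. A reader might infer that Phase 2 has half the patients it needs, but the documents do not support that: it would require the Phase 1 paragraph to be right and the aims and Phase 2 both to be wrong.

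A reduction step could also be drawn in Figure 2, which the protocol says shows item generation and review and which is missing from the copy reviewed. So one can say only that the text contains no such step.

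The target itself is softer in Phase 2, where it is a strong recommendation and the protocol concedes that sample-size theory for item response models is largely lacking. In the aims, however, the same number is described as needed.

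A reader might further infer, from the rule that recalls only a participant who "cannot complete more than 60 items in one session", that patients stopping between 61 and 99 items will pull the average well below 100. The rule does not guarantee 100 per patient, but the same section plans for about 100 on average, and nothing in the document supports a lower average. Raising the recall threshold would also work against the endurance limit, so it is not a clear improvement.

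Finally, the consequences are indirect. The Phase 6 primary outcomes are ADL measures, and in Phase 4 both arms take the same test from blinded assessors. Noisier calibration would mainly cost precision; no bias between arms is shown.

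**Conclusion.** The contradiction is real: 200 items per pool and 400 in total in the Phase 1 procedures, against 100 and 200 in the aims and Phase 2. The Phase 2 sample of 400 gives the stated 200 patient responses per item only with 200 items. The halving to about 100 per item is conditional on 400 items actually being fielded, and the 41% increase in standard error further assumes calibration on patients alone. Separately, and at lower weight, with 200 items the target is an expected value that about 48% of items would miss under simple random selection, assuming that each patient completes 100 items. This is an inconsistency to correct before Phase 2 starts.

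**What to change.** 1. In Section E, Phase 1, Procedures of Item Pool Development, change the counts to 100 items per pool and 200 in total. Alternatively, if more items are to be drafted than fielded, state the step that cuts each pool to 100 before Phase 2 and the criteria it uses. Only if 400 items are truly to be fielded would the Phase 2 sample have to be re-derived.
2. In Phase 2, replace simple random selection with a balanced allocation in which each item is assigned to exactly half of the patients (200 of 400). Patients still receive randomly composed sets of about 100 items. Incomplete interviews can still lower the count, but the spread due to chance selection disappears.

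The cost is one corrected sentence or one added one, plus item lists generated in advance. No extra patients, sessions or items per patient are needed.
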